Benefits include: Improved knowledge and insight. Participation might lead patients to have a better understanding of the factors that contribute to their overall well-being. This can be achieved with analysing the six life domains of the positive health conversation tool. This insight might result in appropriate interventions that meet the needs of the hotspotters.

A potential risk that should be taken into account is temporary elevated stress. Hotspotters experience a combination of different problems which can make life more complex and challenging. The heightened emphasis, especially in the beginning, on the factors that contribute to their health and social problems could result in higher stress levels in some participants.

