1. OBJECTIVES

The primary goal of this study is to get insight in the cost-effectiveness after 12 months of working with a proactive, integrated (social) care approach in patients fitting our definition of a hotspotter. A hotspotter is a patient with problems on two out of three health domains (chronic somatic, psychiatric and/or social) and at least 2 acute care activities in the previous 12 months. The medical data from 3 years prior to the start of the study will be used to analyse the costs and utilisation of care. This extended period used for data analysis was deliberately chosen to include a timeframe during and before the SARS-CoV-2 pandemic. Since it is yet unknown how the pandemic and its subsequent measures affected our population and their usage of care.

Hypothesis: We hypothesise that after one year of working with a proactive approach of integrated care to improve the care for patients with problems on two out of three health domains (chronic somatic, psychic and/or social) and at least 2 acute care activities in the previous 12 months will result in reduction in volume and spending of acute care, improvement in experienced health and in patient experience.

Research questions:

Is proactive integrated care cost-effective and result in better patients experience than usual care after 12 months for patients with problems on multiple life domains?

Primary outcomes: Incremental cost-effectiveness from a societal perspective. Information on cost will be based on patient-reported data obtained by questionnaires supplied with data from the GP medical files (*Huisarts informatie system, HIS*) and through CBS microdata. To assess the effectiveness the EQ-5D-5L will be used for determining quality of life.

Secondary outcomes:

Insight into patients experience of care:

Insights into the experiences of care will be gathered during a focus group and information about self-efficacy (PAM-13 and SE+IN itemlist), proactive coping (UPCC), and quality of life (SF-12) will be collected using questionnaires (Hibbard, Mahoney, Stockard, & Tusler, 2005; Bode, & de Ridder, 2008; Turner-Bowker, & Hoque, 2014). A questionnaire on experience of care has been considered, but no validated and appropriate questionnaires for this population are available. Therefore, for insight and rich information on the experienced care the format of a focus group was chosen.

Process evaluation:

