All clusters start to collect control data at the same time ($t=0$). The 20 clusters will be divided into four groups evenly and each group will be randomly assigned one of four time points at which they will start to implement the proactive integrated care intervention. The first switch will be after 2 months ($t=2$). Every subsequent 2 months a next group of general practices will switch to the intervention mode until all groups have started the intervention. All groups will continue with the intervention as described in this protocol for a total of 12 months. After the 12 months of intervention, care will be delivered as usual. There is no objection if care providers and patients wish to maintain certain aspects of the intervention. All measurements and timepoints after the switch to the intervention falls under the intervention period. The total duration of this study comprises 22 months. This results in varying control period ranging from 2 to 8 months. The total of intervention and follow-up period vary from 14 to 20 months. This time table is summarized in the following chart.

In order to achieve more accurate answers from patients and in turn more reliable results, a member of the research team will administer the SF-12, and questionnaires on proactive coping (UPCC), and self-efficacy (PAM-13 and SE+IN) during a face to face interview, as these might require extra guidance when filling in. This will be done at three time points for each group (before the start of the intervention, at the end of the intervention, and two months after the intervention has ended).

[figure not shown]

Figure 1. This figure depicts the time schedule of this study. The EQ-5D-5L is administered 7 or 8 times, depending on cluster, and is depicted as a square. The Care and Work questionnaire is depicted with an arrow. The questionnaires PAM, SE+IN, SF-12 and UPCC are administered thrice: at the start and end of intervention and two months after ending the intervention (star). The dot represents the HCCQ and adapted NPS at 6 months after the start of the intervention. Focus groups (triangle) are organised per cluster, after finishing the intervention.

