4.5 Investigational treatment

The proactive integrated care intervention that will be used consists of five steps:

1. Active invitation of the patient from the practice

2. Consult of 45 minutes with a trained Practice Nurse Mental Health Care based on the Positive Health Methodology. The outcome of this consultation is a spiderweb with an overview of current health status according to positive health methodology.
3. Multidisciplinary Team meeting (MDO) based on the spider web with the domain specific explanation. In this MDO at least the mental health practice nurse, GP, social worker or community nurse are present. The patient is always invited. The outcome of this meeting is: (1) a personalised care plan; (2) appointment of one care coordinator and (3) a structured follow up plan (frequency and duration) of the progression of this patient's problems.
4. Execution of the personalised care plan. The care coordinator has frequent contact with the patient. A minimum of 3 consultations for the first 12 weeks is set, however more frequent consultation can be expected. The proactive nature of this contact is emphasized. A minimum of 4 consultations between patient and care coordinator is set. These minimum amount of consultation is deliberately set to take frequency of consultation as an outcome parameter. The proactive nature will be strongly endorsed, however implementation may differ according to the needs of each individual patient. Given the complex nature of the population the frequency of contact is expected to be higher in the majority.
5. Follow-up of the personalised care plan. During the regular monthly meetings of the health and social care network the follow-up of the patients will be reviewed. Each patient will be discussed at least two times, but more often if necessary. In case the care plan is not followed correctly or it does not have the desired outcome, the patient and the care network will make the needed adjustments to the care plan.

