6. STATISTICAL ANALYSIS

Before analysis, all data will be cleaned improving data quality.

Quantitative data:

We will conduct intention-to-treat and per protocol analysis. We will use multilevel generalized linear models with the patient as the first level to correct for the repeated measures. The GP-practice (or cluster) will be the second level, and the group in which the GP practice is randomized will be the third level. We will adjust for level of integration, neighbourhood, time from start of study (continuous; with an interaction between cluster and time so that each cluster had its own underlying time trend), and total time on the randomised intervention, with time before intervention given as zero (continuous). Based on ICPC-codes used to select eligible patients, we will explore if subgroups can be identified in mainly (chronic) somatic, mainly mental or mainly social problems. Furthermore, analyses/ results will be stratification for sex. The analysis of the implementation will be descriptive.

Cost-effectiveness analysis/budget impact analysis:

The economic evaluation will consist of a trial-based cost-utility analysis (cost per QALY) with a time horizon of one year and a cost-utility analysis with a lifetime horizon (cost per QALY). Both analyses will be performed from a societal perspective. Next to this a Budget Impact Analysis will be performed according to the ISPOR Task Force principles.

Qualitative data:

Qualitative data will be collected through interviews or focus groups with care providers and patients and audiorecording. The interviews and focus groups will be conducted using a topic list based on experience of the pilot (protocol number **NL8223-10216**) and literature, to determine their satisfaction with the new approach.

The collected qualitative data will be analysed using both an inductive and deductive approach. This will be done by first transcribing the data and doing a thematic content analysis. After this, the data will be put into an initial coding book and further analysed until a final coding book is formed. The deductive analysis will be done using the positive health methodology. We will analyze whether positive health topics and techniques are being discussed and applied, as recommended by the methodology.

The audiotapes will be scored by two independent observers using the validated OPTION5 questionnaire.

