7.3 Benefits and risks assessment, group relatedness

Participation in this study is expected to be low risk for the patients. However, both risks and benefits are associated with participation.

Benefits include: Improved knowledge and insight. Participation might lead patients to have a better understanding of the factors that contribute to their overall well-being. This can be achieved with analysing the six life domains of the positive health conversation tool. This insight might result in appropriate interventions that meet the needs of these patients.

A potential risk that should be taken into account is temporary elevated stress. The patients participating in this study experience a combination of different problems which can make life

more complex and challenging. The heightened emphasis, especially in the beginning, on the factors that contribute to their health and social problems could result in higher stress levels in some participants.

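### Section 6 lists time on intervention as the only term separating intervention from control; fitted that way, the EQ-5D-5L models mostly understate, and can reverse, a benefit that comes early and holds

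*Protocol*

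**What the plan says.** Protocol section 6 plans multilevel generalized linear models with levels for patient, practice and randomised group. The listed terms are level of integration, neighbourhood, continuous time from study start with its own trend in each cluster, and "total time on the randomised intervention, with time before intervention given as zero (continuous". It names no on/off, categorical or spline term for the intervention.

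Other parts of the protocol bear on the shape of the effect:
- Section 4.5 loads contact with the care coordinator early: "A minimum of 3 consultations for the first 12 weeks is set", and overall "A minimum of 4 consultations between patient and care coordinator is set".
- Section 3 ends the intervention: "After the 12 months of intervention, care will be delivered as usual". It also says: "All measurements and timepoints after the switch to the intervention falls under the intervention period". Neither section 3 nor section 6 says whether time on intervention keeps counting after month 12.
- The Summary and section 7.3 name an early risk: "A potential risk that should be taken into account is temporary elevated stress".
- The hypothesis under Objectives is that one year of the approach gives "reduction in volume and spending of acute care, improvement in experienced health and in patient experience".

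**The concern.** A term that is zero up to the switch and then rises in a straight line can represent only an effect that starts at nothing and grows steadily. At least three of the minimum four coordinator contacts fall in the first 12 weeks, so a benefit that appears early and then holds is a realistic shape. The cluster-specific trends make matters worse. The fitted mean is a broken line with its bend at the switch. A jump followed by a plateau is fitted by tilting the control-period line upward and bending it down afterwards, so the change of slope can come out negative although the patients improved.

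The hypothesis is about experienced health after one year, so the 12-month effect is the natural quantity to read from these models. At stake is a real EQ-5D-5L gain that is lost or reported with the wrong sign. A smaller matter is a transient early dip, which the same model would turn into a false 12-month gain if a visit caught it.

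**Working it through.** **Inputs from the protocol.** Switches are at t = 2, 4, 6 and 8 months (section 3). There are 7 or 8 EQ-5D-5L visits per patient (sections 3 and 5.1.1). Sections 3, 5.1.1 and 5.3 together place five of them, with s the switch month: t = 0, s (before the start), s+6, s+12 and s+14. For the last, section 5.1.1 says three months after the end for the face-to-face questionnaires, while sections 3 and 5.3 say two; two is used.

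**Assumption.** The other two or three visits are in Figure 1, which is not shown. They were placed at whole months 1-5 or 7-11 after the switch: two of these ten plus t = 22 (45 schedules), three of the ten (120), or two of the ten plus one mid-control visit in groups 2-4 (45). That makes 210. Weighting them equally has no basis in the protocol, so the ranges matter more than the medians.

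**Models.** Practices in a group share visit times, so the mean is written by group g. Let E = max(t - s, 0), either uncapped or held at 12 after month 12.
- As listed: a_g + c_g t + θE; 12-month effect = 12θ.
- With an on/off term: a_g + c_g t + δ·I(t > s) + θE; 12-month effect = δ + 12θ.

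The expected coefficients are (X'V⁻¹X)⁻¹X'V⁻¹μ. Here μ is the true mean profile, and V is the identity or AR(1) with correlation 0.8 per month (assumption).

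**True profiles.** Early lasting benefit: +b from the switch on. First-visit dip: -d at the first post-switch visit, then zero. Gradual benefit: a straight rise to its full value at month 12, then flat.

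**Fitted 12-month effect, range over 210 schedules** (b or d = 1; gradual benefit as a fraction of its 12-month value):

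| Profile (truth at 12 months) | Independent, uncapped | Independent, capped | AR 0.8, uncapped | AR 0.8, capped |
|---|---|---|---|---|
| As listed: early lasting benefit (1) | -1.10 to +0.36 | -0.89 to +1.12 | -0.03 to +0.58 | +0.53 to +1.01 |
| As listed: first-visit dip (0) | +0.78 to +1.38 | +0.17 to +1.45 | +0.20 to +0.52 | +0.09 to +0.42 |
| As listed: gradual benefit (1) | 0.60 to 0.89 | 1.00 | 0.68 to 0.83 | 1.00 |
| With on/off: early lasting benefit (1) | 1.00 | 1.00 | 1.00 | 1.00 |
| With on/off: first-visit dip (0) | -0.03 to +0.10 | +0.15 to +0.49 | -0.79 to -0.21 | -0.29 to +0.16 |
| With on/off: gradual benefit (1) | 0.92 to 0.97 | 1.00 | 0.72 to 0.89 | 1.00 |

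For the early lasting benefit as listed, with independent residuals, the median is -0.54b uncapped (negative in 187 of 210 schedules) and +0.04b capped.

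**Checks.** One schedule (3, 6, 9, 12 and 14 months after the switch, plus t = 22) was refitted with random patient, cluster and group intercepts and 20 cluster slopes. The early lasting benefit came back as -0.53b to -0.51b uncapped and +0.59b to +0.60b capped; under AR 0.8, as +0.17b to +0.18b and +0.87b to +0.88b. A separate set-up used 20 clusters of 10, two other visit schedules, common or cluster trends, and capped or uncapped exposure. There a sustained +0.06 was fitted as -0.076 to +0.009.

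**Size of the dip problem (assumptions).** If 10-30% of patients lose 0.05-0.15 utility, d = 0.10 x 0.05 = 0.005 to 0.30 x 0.15 = 0.045. The median multiplier for a first-visit dip (independent, uncapped) is 1.04, so the false gain is 0.005 to 0.047. The median standard error is 1.69 residual-SD units. With 200/4 = 50 patients per group and a residual SD of 0.15-0.20, that is 1.69/√50 x 0.15 to 0.20 = 0.036 to 0.048. Hence at most 0.047/0.048 to 0.047/0.036, about 1.0 to 1.3 standard errors. The false gain is zero if no visit falls in the episode: 156 of 210 schedules for a 1-month episode, 77 of 210 for a 3-month one.

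**The case against.** The strongest reply is that section 6 gives an adjustment list, and such a list need not name the treatment contrast itself. The same section promises intention-to-treat and per-protocol analyses, which presuppose a contrast, and section 3 classifies every measurement after the switch as intervention. An on/off term may therefore be intended, and a separate analysis plan could spell it out. That reading is plausible, and with such a term an early lasting benefit is returned exactly.

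It does not clear the text. Beside linear exposure, the on/off coefficient alone is the effect at the switch. For a gradually building benefit, uncapped and with independent residuals, its median is only about 0.06 of the 12-month value. The 12-month effect still has to be defined, and so does the treatment of exposure after month 12.

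Three further objections stand. The visit months are assumed. The protocol never says that 12 x slope is what will be reported; that is inferred from the one-year hypothesis. And the primary outcome, incremental cost-effectiveness, is described separately as cost per QALY, so QALYs summed from observed utilities need not pass through this model.

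**Conclusion.** The concern holds for the repeated EQ-5D-5L models if they are fitted with the listed terms alone. An early lasting benefit is mostly understated and can be reversed. With strong serial correlation and exposure capped at 12 months, the error shrinks to +0.53b to +1.01b. All sizes rest on assumed visit months and residual correlation.

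A reader might infer more, and the documents do not support it:
- That the trial expects early harm and will report it as benefit. The Summary and section 7.3 name only a potential risk in some participants ("The heightened emphasis, especially in the beginning, on the factors that contribute to their health and social problems could result in higher stress levels"). The false gain needs a visit inside the episode, and for a first-visit dip its median is at most about 1.0 to 1.3 standard errors.
- That an on/off term is ruled out. Section 6 does not name one, but does not exclude one.
- That the cost-effectiveness result is compromised. This does not necessarily follow.

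**What to change.** In section 6:
1. Name an on/off intervention term beside time on intervention.
2. State whether exposure counts past month 12.
3. Define the 12-month effect as on/off coefficient + 12 x slope.
4. Add categorical time since switch (first post-switch visit, later visits to month 6, months 7-12, after month 12) as a sensitivity analysis only.

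This takes a few sentences and no new data. The standard error rises by up to about 28% over the linear-only model. An error remains for a first-visit dip: about -0.03d to +0.10d uncapped or +0.15d to +0.49d capped with independent residuals, and -0.79d to -0.21d uncapped with serial correlation 0.8. An effect that stops when care returns to usual is not fitted well either. The same projection (independent residuals) returns about 0.5 to 0.7 of it uncapped and 1.5 to 2.1 capped, which is why the sensitivity analysis splits at month 12.

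The categorical form should not be the main analysis. Cut at the first visit and month 6, it is exact for effects that change only at those cuts. But it returns a gradual benefit at a median of 0.53 of its value, and a dip lasting through month 9 as a median false harm of -1.40d. Splitting at month 12 barely changes this (0.57 and -1.32d).

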6.1 AEs, SAEs and SUSARs

6.1.1 Adverse events (AEs)

Due to the high amount of expected (serious) adverse events caused by treatment of the patients as part of standard care, only study related (S)AE's will be reported immediately. This means all (S)AE's related to participation in this study protocol, meaning from filling in the questionnaires, will be reported. All other (S)AE's will not be reported, as no patient benefit is expected from this.

The sponsor will report the intervention related (S)AEs through the web portal *ToetsingOnline* to the accredited METC that approved the protocol, within 7 days of first knowledge for SAEs that result in death or are life threatening followed by a period of maximum of 8 days to complete the initial preliminary report. All other SAEs will be reported within a period of maximum 15 days after the sponsor has first knowledge of the serious adverse events.

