5.7 Premature termination of the study

This is not applicable to this study. There are no health risks associated with study.

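### Section 6.1.1 defines reportable events in two incompatible ways, questionnaire-related only and then intervention-related, so serious events attributed to the intervention could go unreported

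*Protocol*

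**What the plan says.** Section 6.1.1 has two paragraphs on what is reported.

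- **First paragraph.** Because many events are expected from standard care, "only study related (S)AE's will be reported immediately". The term is then explained: "meaning from filling in the questionnaires, will be reported". The paragraph ends by closing the scope: "All other (S)AE's will not be reported, as no patient benefit is expected from this".
- **Second paragraph.** "The sponsor will report the intervention related (S)AEs through the web portal" of the ethics committee. Fatal or life-threatening events have a 7-day limit, with up to 8 more days to complete the report. Other serious events have 15 days.

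Three further places bear on this.

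- **Section 7.3** names one risk: "A potential risk that should be taken into account is temporary elevated stress". It gives the mechanism: "The heightened emphasis, especially in the beginning, on the factors that contribute to their health and social problems could result in higher stress levels".
- **Section 5.7**, explaining why premature termination is not applicable, says: "There are no health risks associated with study".
- **Section 8.4** lists serious adverse events and reactions among the contents of the annual progress report and does not limit them to questionnaires.

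**The concern.** A reporting rule has to tell a practice, for any given event, whether to send it on. Here the answer for an intervention-related event depends on which paragraph is read.

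The reason given for selective reporting is the volume of events from standard care. That supports leaving out standard-care events. It gives no reason to leave out events from the intervention, which is not standard care: section 7.1 gives the new intervention and the extra appointments as grounds for treating the study as subject to the Dutch act on research with human subjects.

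At stake is whether the ethics committee hears of a serious event attributed to the intervention, and whether 20 practices apply one rule. The statement that participation is low risk also rests partly on reports that the first paragraph would not require.

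**Working it through.** No arithmetic applies. The check sets the two paragraphs of 6.1.1 side by side for each type of event.

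| Event attributed to | First paragraph | Second paragraph |
|---|---|---|
| Filling in a questionnaire | Reported, immediately | Not mentioned |
| Intake, multidisciplinary meeting or coordinator contact | Not reported | Reported, 7 or 15 days if serious |
| Standard care | Not reported | Not mentioned |

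**Step 1: is there a true conflict?** Yes, in the second row. The same event is excluded by one paragraph and required by the other. The third row raises no conflict.

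**Step 2: can the wording be read so that both hold?**
- If the second paragraph uses intervention-related loosely, as another name for study-related, the questionnaire definition carries over and intervention events are excluded. The words then do not mean what they say.
- If the questionnaire phrase is only an example, the first paragraph does not say so. It is worded as a definition, and the exclusion of everything else follows it directly.
- If the first paragraph concerns only immediate reporting, with section 8.4 covering the rest once a year, the closing exclusion should carry that limit. It has none. The second paragraph's 7- and 15-day limits are also not annual reporting.

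None of these readings removes the conflict.

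**Step 3: where does the named risk sit?** Section 7.3 speaks of risks of participation, and its risk sentence does not name the intervention. The preceding paragraph of 7.3 concerns the Positive Health conversation tool. In section 4.5 that method is the basis of the 45-minute intake early in the intervention. The mechanism in 7.3 is attention to the causes of the patient's problems, mainly at the beginning. That fits the intake better than the questionnaires. It is an inference, though a strong one.

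**Step 4: do other data fill the gap?** Only in part.
- Acute care use is obtained per patient from practice records and national statistics (5.1.1), at the start and end of the study, without a judgement of cause. It cannot serve a 7- or 15-day duty.
- The EQ-5D-5L is taken 7 or 8 times and the SF-12 three times. Neither attributes a change to a particular event.
- A reason for withdrawal is asked for but need not be given (5.4.1), and data collection stops when a participant leaves the study (5.6).

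**Step 5: do the other sections agree?** Section 5.7 denies any health risk, while 7.3 names one. Section 8.4 promises serious events without the questionnaire limit, but under the first paragraph of 6.1.1 only questionnaire-related ones would have been reported.

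**The case against.** Limiting reports to study-related events is a deliberate choice with a stated reason, and a sensible one in patients selected for at least two acute care encounters in a year. The intervention is delivered inside the practice by staff who also give usual care, so separating intervention-related from standard-care events may be hard. The second paragraph does commit to reporting intervention-related events, and if it is followed nothing is lost. The remark in 5.7 is a loose sentence in a section about something else.

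Most of this stands. The choice to exclude standard-care events is not in dispute, and the difficulty of attribution is a real cost of the fix. It does not remove the conflict, since the second paragraph already requires that judgement.

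A reader might go further and infer that harms of the intervention would go unrecorded and that the trial could say nothing about harm. The protocol does not support this. Section 6.1.1 governs what is reported and is silent on what is recorded. Section 8.4 lists serious events without the questionnaire limit. Acute care use, EQ-5D-5L (with its anxiety/depression dimension), SF-12 and the patient focus groups could all show worsening, though without attribution. A reader might also take 7.3 as stating that the intervention causes the stress; it does not say so.

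Nor do contact times measure a loss of surveillance. Setting the 170 minutes of questionnaires in section 5.3 against the hours of intervention contact counts no missed event, and it assumes that the first paragraph prevails, which is the open question.

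**Conclusion.** The point holds as an internal contradiction in a safety rule. As written, 6.1.1 gives opposite instructions for intervention-related events, and no other section resolves them. If the first paragraph is followed, serious events attributed to the intervention could go unreported.

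The size cannot be put as a number, because the protocol gives no rate for such events. The reach is the whole trial: 20 practices and 200 planned patients, each due to cross over to a 12-month intervention.

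The conclusion rests on the plain wording of the two paragraphs. It does not depend on the inference that links the stress risk to the intake; that inference only shows why the excluded category matters. The cost-effectiveness estimate, its power and its analysis are untouched. The text should be corrected because the ethics committee and the practices need one rule.

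**What to change.** Replace the two paragraphs of 6.1.1 with one definition of a reportable event and use it throughout:

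- Include events related to the intervention, as the second paragraph already commits, and events related to the questionnaires.
- Keep events from standard care excluded, with the existing reason.
- State that the reporting route and time limits already in the section apply to both included categories.
- Align the statement on health risks in 5.7 with the risk named in 7.3.
- State in 8.4 that the annual report uses the same definition, or say expressly where it is wider.

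The cost is a wording amendment, plus added work to judge whether an event is related to the intervention or to standard care. The number of extra reports cannot be estimated from the protocol. The change affects no sample size, outcome or analysis.
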